9. RESEARCH METHODS

9.1 Study Design

This study is a post-authorization, prospective, uncontrolled, non-interventional, multicenter cohort study. Approximately 80 subjects with congenital hemophilia B will be enrolled. Subjects must be prescribed rFIX (RIXUBIS) by the treating physician before study participation. Data will be collected over a period of 4 years from the time of study enrollment. The treating physician will determine the treatment regimen, as well as the frequency of laboratory, radiological, and clinical assessment according to her/his routine. Data will be collected on routinely scheduled and emergency visits. There is no binding visit schedule, however it is recommended that the subjects have at least annual visits. Available data from these visits shall be transcribed onto the electronic case report forms (e-CRFs).

It is considered standard practice for subjects with hemophilia to maintain a diary either on paper or in an electronic form (e.g. Smart Medication) which captures FIX treatment and disease related data. A subject diary will be provided to each subject to assist with the standardization of data collection as stated in Section 9.4.2. Nevertheless, the completion of the diary is a voluntary effort by the individual subject or subject's legally authorized representative. All bleeding events and their treatment recorded in subject diaries during study participation period will be transcribed onto e-CRFs.

QoL questionnaires will be provided at baseline and on an annual basis to subjects or their legally authorized representatives.

As no hypothesis testing or interval estimation will be applied, the sample size for the study is not based on statistical considerations.

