 - FIX regimen used at the time of inhibitor detection
 - Maximum historical titer
 - Local laboratory cut off value for positive inhibitor titer
 - History of ITI therapy, if any, including FIX product and regimen used.
 - Date(s) of inhibitor disappearance
 - Most recent FIX inhibitor test results.
- Current RIXUBIS treatment
 - Dosage and dosing intervals
 - Regimen start date

- Total EDs to RIXUBIS at screening visit
Where exact numbers of EDs is not available, one of the following ranges should be selected: 0, 1-4, 5-20, 21-50, 51-100, 101-150 or >150.
- FIX product used prior to RIXUBIS treatment initiation (maximal retrospective time-period of 12 months before treatment initiation)
 - Name of product, dosage and dosing interval
 - Regimen start and end date
 - Total EDs to FIX products at screening visit
Where exact numbers of EDs is not available, one of the following ranges should be selected: 0, 1-4, 5-20, 21-50, 51-100, 101-150 or >150.
- Sporting activities (type and frequency)
- Ambulatory status, including need for ambulatory assistance devices such as leg braces, cane, crutches, or wheelchair
- Number of bleeding episodes (ABR and annualized joint bleeding rate (ABJR)) categorized by severity within the last 12 months.
- Status of joint health as assessed by physical exam at study enrollment
+ Musculoskeletal evaluation of target joints using HJHS within the last 5 years prior to study enrollment.
- Status of joint health assessed by imaging techniques (e.g. MRI or X-ray)
+radiological evaluation of any joints using the Petterson score within the last 5 years prior to study enrollment.

The following data, if available will be collected at interval and termination visits:

- Total EDs to RIXUBIS since the last visit
- Current RIXUBIS treatment regime (if changed):
 - Dosage and dosing intervals
 - Regimen change date
- Height, Body weight
- FIX inhibitor titer
- Bleed occurrence, including location, etiology, and severity

- Status of joint health as assessed by physical exam
+ Musculoskeletal evaluation of target joints using the HJHS.
- Status of joint health as assessed by imaging techniques (e.g. MRI, X-ray)
+ Radiological evaluation of any joints using the Pettersson score.
- HRQOL measures, surgical data and activity levels (including sporting activities)

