9.3 Variables

9.3.1 Variables for assessing the primary endpoint

9.3.1.1 Effectiveness of prophylaxis

- Effectiveness as measured by
 - Overall effectiveness assessment for the prevention of bleeding
 - ABR and monthly bleeding rate (MBR), all bleeds
 - AJBR, monthly joint bleeding rate, all joint bleeding events
 - ABR, MBR, trauma related
 - Overall effectiveness assessment for prophylaxis with an “excellent-to-poor” 4-point scale, as rated by the patients or care-giver (for details, see Appendix 1, [Table 4](#)).

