9.7.3.2 Methods of Analysis for Effectiveness Endpoints

The method of analysis will be applied to the effectiveness endpoint. The primary endpoint, ABR of all types of bleeding episodes, will be calculated for each subject and described for prophylaxis.

In addition, separate description of ABR will be provided for each of the following treatment regimens, assuming a minimum observed period of (≥ 90 days) is fulfilled:

- Standard prophylaxis
- On-demand treatment
- Episodic prophylaxis
- ITI

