Good	Definite pain relief and/or improvement in signs of bleeding within approximately 6 hours to 24 hours requiring more than 2 infusions for complete resolution. Administration of further infusions to maintain hemostasis would not affect this scoring.
Fair	Probable and/or slight relief of pain and slight improvement in signs of bleeding within approximately 6 hours to 24 hours. Requires multiple infusions for complete resolution.
Poor	No improvement of signs or symptoms or conditions worsen.

For prevention of bleeding episodes:

Annualized (ABR) and/or monthly bleeding rate (MBR), all bleeds, will be calculated as appropriate, based on the following formula: $ABR = (\text{number of bleeds/observational period days}) \times 365.25$; $MBR = (\text{number of bleeds/observational period} - \text{days}) \times 30.44$

- ✓ ABR and/or MBR will be calculated as appropriate, in all joint bleeding events
- ✓ Assessment of hemostatic effectiveness
 - The effectiveness will be assessed by a “excellent-to-poor” 4-point Likert scale by the subjects/care-giver (subjects <12 years: care-giver, subjects ≥ 12 years: self assessment) at the end of each prophylaxis period (if possible rated within 24 hours from the end of the prophylactic treatment) or on an annual basis, whichever occurs first.

Table 4 Overall Effectiveness Assessment for Prophylaxis Therapy	
Excellent	Definitely low bleeding rate with improvement in daily activities and quality of life. Very satisfied with the treatment and worth being continued-
Good	Relatively low bleeding rate with some improvement in daily activities and quality of life. Satisfied with the treatment and worth being continued-
Fair	Relative increase in breakthrough bleeding episodes with only partial benefit in terms of activity level and quality of life. Partially satisfied with the treatment. Not sure if it is worth continuing treatment
Poor	Frequent breakthrough bleeding episodes interfering with activity level and quality of life. Not satisfied with the treatment.

APPENDIX 2

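### The prophylaxis rating scale has no category that fully fits a subject with low or zero bleeding whose activity and quality of life are maintained rather than improved, and it gives no reference point for improvement

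*Protocol*

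**What the plan says.** Protocol section 9.3.1.1, under the variables for the primary endpoint, includes this item: "Overall effectiveness assessment for prophylaxis with an “excellent-to-poor” 4-point scale, as rated by the patients or care-giver". It refers to Appendix 1, Table 4. Section 9.7.3.2 names the endpoint itself: "The primary endpoint, ABR of all types of bleeding episodes, will be calculated for each subject and described for prophylaxis".

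The first sentence of each Table 4 anchor reads:

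- Excellent: "Definitely low bleeding rate with improvement in daily activities and quality of life"
- Good: "Relatively low bleeding rate with some improvement in daily activities and quality of life"
- Fair: "Relative increase in breakthrough bleeding episodes with only partial benefit in terms of activity level and quality of life"
- Poor: "Frequent breakthrough bleeding episodes interfering with activity level and quality of life"

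Each anchor then adds a statement of satisfaction. Excellent and Good express high or ordinary satisfaction and regard the treatment as worth continuing. Fair expresses partial satisfaction and doubt about continuing. Poor expresses dissatisfaction.

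Appendix 1 has the rating made at the end of each prophylaxis period or yearly, whichever comes first. Subjects aged 12 or over rate themselves, and caregivers rate younger children.

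On who enters, section 9.1 says: "Subjects must be prescribed rFIX (RIXUBIS) by the treating physician before study participation". Section 9.2.6 records at screening "Total EDs to RIXUBIS at screening visit", as well as the FIX product, dosage and interval used before RIXUBIS, looking back at most 12 months before RIXUBIS was started.

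**The concern.** The top two anchors describe a low bleeding rate together with a change for the better. The lower two describe more bleeding or frequent bleeding. The table does not provide for a low bleeding rate with activity and quality of life held at an already good level. For a subject who comes from effective prophylaxis, that is what successful prevention looks like.

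Improvement and increase are both relative terms, but Table 4 names no comparison time. Section 9.7.3.4.4 does name one for the quality-of-life, pain and activity measures, which are summarised as changes from baseline.

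What is at stake is the meaning of the rating distribution. If the top categories depend on improvement, two subjects with the same bleeding control can be rated differently because one switched from on-demand treatment and the other was already on prophylaxis. Raters will also resolve the mismatch in different ways. An analysis plan cannot repair this, because the anchors act when the rating is made.

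**Working it through.** There is no stated figure to reproduce. The check sets the anchors against the states a subject can be in.

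**Step 1: which states match an anchor.** Take three bleeding states from the anchors (low or zero; relative increase; frequent). Cross them with four activity and quality-of-life states (improved; unchanged; partial benefit; interference). The first sentence of each anchor gives:

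| Bleeding | Improved | Unchanged | Partial benefit | Interference |
|---|---|---|---|---|
| Low or zero | Excellent or Good | none | none | none |
| Relative increase | none | none | Fair | none |
| Frequent | none | none | none | Poor |

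Three of the 12 cells match. The grid is this review's construction, and several empty cells are rare or odd combinations, so 3 of 12 does not measure how large the problem is. The cell that matters is low or zero bleeding with unchanged activity and quality of life, which is a plausible good outcome and is empty.

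**Step 2: does the satisfaction wording fill that cell?** Take a very satisfied subject with no bleeds and stable activity. Of the three elements of Excellent (bleeding, activity and quality of life, satisfaction), two match and one does not. For Fair and Poor, all three conflict. The wording therefore points upwards, but no anchor fits in full.

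**Step 3: does the gap depend on prior regimen?** Section 7.2 reports that, in the earlier RIXUBIS study, subjects who moved to prophylaxis from on-demand or intermittent treatment had more pronounced quality-of-life gains. Section 9.7.1 defines a dataset for subjects switching from on-demand to prophylaxis, so a mixed population is foreseen. A scale that makes improvement a condition of the top ratings will tend to favour switchers at equal bleeding control.

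**Step 4: scale, for context only.** Section 7.2 gives 24 of 56 prophylaxis subjects without bleeds: 24/56 = 42.9%, exact (Clopper-Pearson) 95% interval 29.7% to 56.8%. Suppose that share applied here (an assumption):

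- All 80 subjects on prophylaxis: 80 × 0.429 ≈ 34 bleed-free (24 to 45).
- 40 subjects on prophylaxis: 40 × 0.429 ≈ 17 bleed-free (12 to 23).

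These are counts of bleed-free subjects, not of subjects without a category. Among the bleed-free, only those whose activity and quality of life did not improve fall in the gap, and the documents do not give that share.

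**The case against.** The strongest reply is that this is an overall rating by patients and caregivers. They will read each anchor as a whole, and a contented subject without bleeds will choose Excellent or Good. Much of that stands: the satisfaction text gives real guidance and makes it unlikely that many such subjects would choose Fair or Poor. It does not remove the mismatch, since the rater must disregard one element of the chosen anchor, and choosing between Excellent and Good is then left to the individual.

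Three stronger readings are tempting, and the documents do not support them.

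- A reader might infer that the primary objective goes unanswered. Section 9.7.3.2 makes ABR the primary endpoint, and section 9.3.1.1 also lists monthly, joint and trauma-related bleeding rates. None of these uses Table 4.
- A reader might infer that a subject who improves in the first year and holds the gain cannot be Excellent or Good in years 2 to 4. That assumes improvement means change since the last rating. It can equally mean benefit from treatment, a reading that the partial-benefit wording under Fair supports. The text is ambiguous and does not exclude such subjects.
- A reader might count unclassifiable ratings, for example half of 80 subjects with four yearly ratings each: 0.5 × 80 × 4 = 160. The half is an assumption with no source in the protocol, and the product also needs complete follow-up, no change of regimen and no improvement in anyone. The 43% bleed-free share does not help, because section 7.2 reports improved quality of life in that same study. Nor does the top exposure range at screening (more than 150 days): it is one option in a list that starts at 0 and does not show that long-term users will enrol.

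**Conclusion.** The point holds as a defect of wording in one of several variables listed for the primary endpoint. No Table 4 category fully describes low or zero bleeding with maintained activity and quality of life, and no reference point is given for improvement or increase. No other part of the protocol repairs this.

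The consequence is that ratings may differ by prior regimen and by rater at equal bleeding control. ABR and the other bleeding rates are untouched. The size cannot be stated: the number affected depends on how many subjects enter on established, effective prophylaxis and do not improve further, and the protocol gives neither figure. The conclusion rests only on the wording of the anchors and on such subjects being eligible, which sections 9.1 and 9.2.6 allow.

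The change is worth making because it is cheap and ratings given under the present anchors cannot be re-coded afterwards.

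**What to change.** Reword three anchors in Table 4, keeping the satisfaction sentences:

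- Excellent: *definitely low bleeding rate with improved or maintained good daily activities and quality of life*
- Good: *relatively low bleeding rate with some improvement or a maintained level*
- Fair: *some breakthrough bleeding with only partial benefit*, with no increase required

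State one fixed reference point for improvement, for example status before starting RIXUBIS prophylaxis. The previous rating should not be used as the reference, because that would turn the scale into a year-on-year change score and penalise a gain that is held.

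Optionally, tabulate the ratings by the prior regimen that section 9.2.6 already collects. This is a presentation choice that can sit in the analysis plan.

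The cost is new text in one table and in whichever form carries the rating (the diary contents listed in section 9.4.2 do not include it). Two small downsides follow. The wording will differ from any earlier use of the scale, and a fixed reference asks subjects with long prior use of the product to recall an earlier state.
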